# 6. STUDY POPULATION

## 6.1 Inclusion Criteria

Individuals will be assessed for study eligibility based on the criteria presented below. Unless specified otherwise, ocular criteria refer to the study eye only.

- 1. 21 years of age or older, male or female.
- 2. Able to understand study requirements, willing to follow study instructions, provide written informed consent, and comply with all study requirements, including required study follow-up visits.
- 3. Diagnosis of OAG, including pseudoexfoliation glaucoma and pigmentary glaucoma, which meets diagnostic criteria defined below:
  - Vertical cup-to-disc ratio (C:D) on fundoscopic exam of at least 0.6, or
  - Heidelberg Retinal Tomograph (HRT) of good quality demonstrating a Moorfield Regression Analysis that is "outside normal limits", or
  - Optical Coherence Tomography (OCT) demonstrating a thinness of the nerve fiber layer at the p < 5% level as defined by the instrument's built-in age-adjusted normative database.
  - Glaucoma Visual Field (VF) with a Mean Deviation (MD) < 0 dB
- 4. Baseline unmedicated IOP of 21 mmHg 36 mmHg. *Note: Subjects who were using ocular hypotensive medication at the time of study enrollment must complete a required medication washout period prior to baseline IOP assessment as specified in Table 7.*
- Gonioscopy confirming normal angle anatomy at site of implantation, and Shaffer grade of ≥ III in at least two quadrants, one of which must be the quadrant of the intended site of implantation.

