## 8. STATISTICAL METHODS

#### 8.1 Sample Size

The primary effectiveness endpoint is the outcome of  $\geq 20\%$  decrease in IOP from baseline without IOP lowering medications up to 12 months post-operatively (IOP response). The proportion of eyes meeting the effectiveness outcome, IOP response rate, will be assessed at 12 months. A sample of at least 101 eyes will be enrolled across the two groups (CyPass only control and CyPass + Healon 5 dose selected) with an estimated 86 eyes completing their month 12 visit. Assuming a 30% success rate for the control eyes and a 60% success rate for the visco-assisted eyes, 80% power can be achieved with 43 eyes per arm using a two-tailed alpha of 0.05.

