2.2 Safety Analysis Set

Safety analyses will be conducted using the safety analysis set on a treatment-emergent basis. The safety analysis set will include all enrolled subjects who undergo CyPass implantation surgery. For treatment-emergent safety analyses, subjects/eyes will be categorized under the actual treatment received. Therefore, subjects/eyes exposed to an incorrect study treatment will be included in the group corresponding to the actual treatment received. All listings of safety data will use the Safety Set.

3 Statistical Methods

Statistical analyses will be performed to summarize the primary and secondary efficacy endpoints as well as key safety evaluations. Additionally, within each treatment, changes from baseline will be assessed where appropriate.

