5.1 Efficacy Endpoints

Primary Efficacy Endpoint

The outcome of \geq 20% decrease in IOP from baseline (unmedicated/Baseline2) up to 12 months post-operatively without IOP lowering medications (IOP response) is determined as follows,

Percent change in IOP from baseline is defined as, for each subject,

$$Percent \ Change = \frac{PostOperative \ IOP - Baseline \ IOP}{Baseline \ IOP} \ge 100$$

such that negative percent changes represent a favorable effect, while positive percent changes represent an unfavorable effect. Therefore, IOP response is achieved if the percent change is $\geq 20\%$ lower than baseline (i.e. the percentage change is $\leq -20\%$).

 IOP response rate: Proportion of eyes meeting the effectiveness outcome is defined as the number of eyes with occurrence of ≥ 20% decrease from baseline divided by the number of eyes having non-missing post-Baseline and Baseline IOP measurements at each the given visit.

While the IOP response rate at 12 months without IOP lowering medications is the primary endpoint, results will be summarized at each postoperative visit relative to unmedicated baseline. Note, at 12 months for subjects being treated with ocular hypotensive medications, a washout for the 12 month assessment was intended to obtain unmedicated IOP measurements. Note: prior to version D of the protocol, the 12 Month Washout visit was not required for the initial dose selection phase subjects who were on IOP lowering medication

Document: TDOC-0053376 Version: 2.0; Most-Recent; Effective; CURRENT

Status: Effective

Secondary Efficacy Endpoints

[figure not shown]
 Rate of intraoperative and post-operative device related ocular adverse events up to 12 months postoperatively

```
Rate = \frac{\text{\# of subjects who experience } either \text{ an intraoperative } and/or \text{ post} - \text{operative device related ocular AE}}{\text{\# of subjects}}
```

such that device related includes definitely, probably, or possibly.

- Mean change in medicated IOP from baseline (Baseline1) to 12 months postoperatively regardless of medications
 - Computed for subjects having both non-missing baseline medicated IOP and
 12 month postoperative regardless of medications measurements.
- Proportion of eyes using ocular hypotensive medications at 12 months postoperatively

```

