5.3 Statistical Methods for Efficacy Analyses

The primary efficacy endpoint, the achievement of a 20% decrease in IOP relative to baseline in the absence of IOP lowering medications up to 12 months post-operatively will be summarized at each post-operative visit by the number and percent of subjects having IOP response and the corresponding 95% confidence interval (CI) based on the exact binomial distribution.

[figure not shown]
Secondary efficacy endpoints describing proportions meeting given criteria will be summarized at each post-operative visit by the number and percentage of responses and the corresponding 95% CI based on the exact binomial distribution. While descriptive statistics for all continuous parameters for the actual values and change from baseline, including the 95% CI of the actual/observed results (based on a *t*-distribution) and change (based on a paired *t*-distribution), will be provided for each protocol specified visit, the 12 month visit is of most interest.

All efficacy analysis summaries will be produced using the FAS set.

Document: TDOC-0053376 Version: 2.0; Most-Recent; Effective; CURRENT

Status: Effective

Document: TDOC-0053376 Version: 2.0; Most-Recent; Effective; CURRENT

Status: Effective

6 Safety Analysis Strategy

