6.3.11 Device Deficiencies

The applicable definition of a device deficiency is in the study protocol. A listing of all device deficiencies, as recorded on the Device Deficiency Log, will be provided.

7 Sample Size and Power Calculations

The primary effectiveness endpoint is the outcome of \geq 20% decrease in IOP from baseline without IOP lowering medications up to 12 months post-operatively (IOP response). The proportion of eyes meeting the effectiveness outcome, IOP response rate, will be assessed at 12 months. A sample of at least 101 eyes will be enrolled across the two groups (CyPass only control and CyPass + Healon 5 dose selected) with an estimated 86 eyes completing their month 12 visit. Assuming a 30% success rate for the control eyes and a 60% success rate for the visco-assisted eyes, 80% power can be achieved with 43 eyes per arm using a two-tailed alpha of 0.05 that is based on the Likelihood Ratio Chi-square test for two proportions. It is

Document: TDOC-0053376 Version: 2.0; Most-Recent; Effective; CURRENT

Status: Effective

estimated that approximately 10% of those receiving the CyPass Micro-Stent may be lost to follow-up.

Document: TDOC-0053376 Version: 2.0; Most-Recent; Effective; CURRENT

Status: Effective

Date/Time (mm/dd/yyyy GMT):	Signed by:	Justification:
05/29/2017 11:06:02		
05/30/2017 18:23:03		
06/05/2017 20:12:51

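### Continuous IOP endpoints get only within-arm intervals in the visible plan, which do not estimate what the viscoelastic adds; state an adjusted 60 µl minus CyPass-alone difference

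*SAP*

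**What the plan says.** SAP 5.3 covers continuous efficacy parameters with "descriptive statistics for all continuous parameters for the actual values and change from baseline". It adds a t-based 95% interval for observed values and a paired-t interval for change, at each visit, with month 12 of most interest. The introduction to SAP section 3 sets the scope: "within each treatment, changes from baseline will be assessed where appropriate". Protocol 8.3 likewise offers a 95% CI for change and names no contrast or model.

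The continuous IOP endpoint named in SAP 5.1 is "Mean change in medicated IOP from baseline (Baseline1) to 12 months postoperatively regardless of medications". SAP 3.2 defines Baseline1 as the Screening reading before any washout and Baseline2 as the unmedicated reading. Change from Baseline2 is summarized in SAP 6.3.4, which also provides side-by-side box plots of CyPass alone and 60 µl. Those plots are the only visible between-arm display of continuous IOP.

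The sample size, by contrast, is comparative. SAP section 7 says "80% power can be achieved with 43 eyes per arm using a two-tailed alpha of 0.05", a figure "that is based on the Likelihood Ratio Chi-square test for two proportions".

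**The concern.** All arms receive the CyPass Micro-Stent, and only the adjunct viscoelastic differs. The randomized comparison exists to isolate that adjunct. A paired-t interval inside one arm mixes several things:

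- the stent effect, which both arms share;
- for IOP regardless of medication, any change in IOP-lowering drugs between Screening and month 12;
- for change from Baseline2, some regression to the mean, because the reading that must meet the entry rule ("Baseline unmedicated IOP of 21 mmHg" up to 36) is also the baseline.

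Both arms could therefore show a clear fall while the report gave no estimate, with its uncertainty, of the difference the trial was randomized to measure.

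**Working it through.** **1. The plan's own figure.** Inputs from Protocol 8.1 and SAP section 7: 30% versus 60%, two-sided alpha 0.05, 43 evaluable eyes per arm. For the likelihood ratio chi-square, with p̄ = 0.45, the noncentrality is 2n × Σ[p ln(p/p̄) + (1−p) ln((1−p)/(1−p̄))] over the two arms. The bracketed terms are 0.04717 and 0.04523.

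- n = 42: noncentrality 7.76, power 79.6%.
- n = 43: noncentrality 7.95, power 80.5%.

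The figure of 43 reproduces, and it is the size for a between-arm test.

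**2. What the within-arm interval can distinguish.** The documents give no IOP SD, correlation or stent effect, so these are assumptions: unselected mean 24 mmHg, SD 4, baseline-to-month-12 correlation r = 0.7, selection on 21 to 36 mmHg, and a 5 mmHg fall from the stent in both arms. There were 4,000 simulated trials with 43 eyes per arm.

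| True viscoelastic effect | Both paired-t intervals exclude zero | ANCOVA rejects | Mean ANCOVA estimate |
|---|---|---|---|
| 0 mmHg | 100% | 4.3% | −0.02 mmHg |
| −2 mmHg | 100% | 89% | −2.00 mmHg |

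With no viscoelastic effect, the mean within-arm change was −5.46 mmHg: the stent's −5, and −0.46 from regression to the mean. The latter agrees with (1 − r) × (mean of selected eyes − unselected mean) = 0.3 × (25.54 − 24) = 0.46.

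**3. Size of regression to the mean.** The same formula with assumed mean 22 to 26, SD 3 to 5 and r 0.6 to 0.8 gives 0.06 to 1.3 mmHg, or 0.2% to 5% of baseline. With no effect of any kind, a paired-t interval from 43 eyes would exclude zero in about 6% to 53% of arms. This applies to change from Baseline2, and to Baseline1 only in eyes unmedicated at Screening, where the two baselines are the same.

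**4. What the adjusted difference would deliver.** Half-width of its 95% CI = t × SD × √(1 − r²) × √(2/n), with t = 1.989 on 83 degrees of freedom and n = 43. Here SD is the month-12 SD; SD 3 to 5 and r 0.3 to 0.7 are assumed.

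- SD 4, r 0.5: 1.989 × 4 × 0.866 × 0.2157 = 1.49 mmHg.
- Range: 0.9 mmHg (SD 3, r 0.7) to 2.0 mmHg (SD 5, r 0.3).
- Difference detectable with 80% power, (1.96 + 0.84) × SD × √(1 − r²) × √(2/n): 1.3 to 2.9 mmHg, and 2.1 mmHg at SD 4, r 0.5.

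**5. Gain over comparing raw change scores.** A model with true IOP mean 22 to 24, SD 4, visit-to-visit SD 2 to 3 mmHg and selection on 21 to 36 mmHg gives correlations of 0.46 to 0.69 among selected eyes. The ratio of ANCOVA to change-score variance is 0.91 to 0.96, so adjustment lowers the variance by 4% to 9%.

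**The case against.** The strongest objection is that the absence is not proven. SAP 5.2 is not in the visible body, entries in the contents are blank around 5.2 and under 5.3, and material is missing after the primary-endpoint paragraph. The likelihood ratio test in SAP section 7 shows that a comparison was contemplated. This stands as a limit: the point can be made only about the visible text. It does not remove the point, because the sentence on continuous parameters and Protocol 8.3 are both readable and neither gives a contrast.

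A second objection is that the trial was powered on a binary response and the IOP means are secondary or supportive. That is fair, and it limits the weight of the point. It does not make a within-arm interval informative about the adjunct.

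Four stronger readings are tempting, and the documents do not support them:

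- That regression to the mean is the main defect. The entry rule acts on Baseline2, whereas the named endpoint uses Baseline1. Regression to the mean is also expected to be alike in randomized arms, so it cancels in a contrast.
- That adjustment buys a large gain in precision. The gain depends on an SD and correlation that the documents do not give. Under the selection model above it is only 4% to 9%, because selection narrows the baseline spread.
- That the plan judges the arms by whether their intervals overlap. No such rule appears.
- That an adjusted difference settles the trial's question at no cost. The trial is unmasked, so medication use after randomization may differ by arm and affect IOP regardless of medication. Before protocol version D the month-12 washout was not required, and nothing is imputed, so some medicated Cohort 1 eyes may have no unmedicated month-12 value.

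**Conclusion.** The point holds for the visible text. The stated analysis of continuous IOP is within-arm, and since both arms receive the stent it cannot estimate what the viscoelastic adds. That conclusion follows from the design and needs no numerical assumption. The simulation illustrates it: the within-arm result was the same (100%) with and without a 2 mmHg viscoelastic effect.

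The planned 43 eyes per arm would support an adjusted difference with a half-width of roughly 0.9 to 2.0 mmHg, on assumed SDs and correlations. This is a worthwhile improvement to secondary and supportive analyses. It is not a flaw in the sample size, which reproduces. If the non-visible parts of SAP section 5 already state a between-arm analysis of continuous IOP, the sponsor need only confirm it.

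**What to change.** First, confirm whether a between-arm analysis of continuous IOP is stated in the parts of SAP section 5 that are not visible. If it is not, change SAP 5.3 as follows:

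- For month-12 IOP, report the ANCOVA-adjusted 60 µl minus CyPass-alone difference with 95% CI on the FAS.
- Use the matching baseline as covariate: Baseline1 for IOP regardless of medication, Baseline2 for unmedicated IOP.
- Include cohort, because allocation ratios differed between cohorts. Include site too, or pool sites if they are small: SAP 1.2 allows up to 10, for about 86 evaluable eyes.
- Show a Cohort 2-only result, because Cohort 1 data informed the choice of 60 µl.
- For number of medications, report the between-arm difference by a method suited to a small count.
- State that IOP regardless of medication reflects drug use after randomization, and report how many Cohort 1 eyes lack a month-12 washout reading.
- Keep the within-arm tables as description. If comparative month-12 data have already been seen, label the addition post hoc.

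The cost is SAP wording and one extra model per endpoint. No subjects, visits or measurements are added.

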6.1 Safety Endpoints

All analyses of safety will be performed on the study eye, with the exception of adverse events, using the Safety Set. Results of safety assessments include the following:

- Adverse events
- Manifest refraction
- Best Corrected Visual Acuity
- Intraocular pressure
- Gonioscopy
- Slit Lamp Examination
- Visual Field
- Dilated fundus examination and C/D ratio
- Secondary Surgical Interventions
- CyPass Explantation and/or Repositioning
- Device deficiencies

6.2 Safety Hypotheses

There are no formal safety hypotheses in this study. The focus of the safety analysis will be a comprehensive descriptive assessment and/or data listings of the safety results listed in Section 6.1.

6.3 Statistical Methods for Safety Analyses

6.3.1 Adverse Events

The applicable definition of an Adverse Event (AE) can be found in the study protocol. All AEs occurring from when a subject signs informed consent to when a subject exits the study will be accounted for in the reporting. A treatment emergent AE (TEAE) is an event on or after the day of surgery.

Document: TDOC-0053376 Version: 2.0; Most-Recent; Effective; CURRENT

Status: Effective

An overall summary of treatment emergent adverse events will be provided including the number and percentage of unique subjects with at least one AE, serious adverse event (SAE), AE leading to withdrawal, non-ocular or ocular, and study eye ocular event. Further, within study eye ocular events, the number and percentage of eyes with at least one: serious ocular event, intraoperative or postoperative ocular event, device related ocular event (definitely, probably, or possibly), serious device related, and serious device related leading to withdrawal. Additionally, for all eyes in the safety set, summarization of unique counts and percentages of ocular AEs by group will be provided separately for intraoperative or postoperative events by the in-house AE coded terms by descending frequency (sorted using overall group frequencies).

All reported adverse events will be detailed in the data listings. Individual subject listings provided will include:

- Ocular AEs for all eyes in the Safety Analysis Set
- Ocular AEs for all eyes not in the Safety Analysis Set
- Non-ocular AEs for all enrolled subjects
- Listing of deaths for all enrolled subjects

These listings will also include AEs that occur after signing the ICF but prior to surgery, if applicable.

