# 7.6 Subject Disposition

#### 7.6.1 Terminated Subjects

Subjects may be terminated (exited) from the study early due to:

- Screen failure
- AE(s)
- Administrative reasons (e.g., voluntary withdrawal, lost to follow-up)

Subjects who are terminated prior to surgery will not be followed beyond the date of termination unless the reason for termination in an IOP-related adverse event (AE). These subjects will be followed until resolution or stabilization of the AE. Subjects who are terminated prior to surgery due to a non-IOP-related AE will not be followed beyond the date of the AE report. Subjects who undergo surgery but do not receive the CyPass due to a surgical AE will be followed until resolution or stabilization of the AE. Subjects who receive the CyPass Micro-Stent but are terminated from the study should be followed for safety until the end of study period.

Study sites must make every attempt to follow-up on subjects who do not return for scheduled study examinations. If a subject is non-responsive to these follow-up attempts, he/she will be considered to be lost to follow-up. The sponsor should be notified promptly regarding subjects who are terminated prior to study completion.

Subjects terminated after implantation of the CyPass Micro-Stent will not be replaced.

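### SAP 6.3.1 ends adverse event reporting at study exit, but protocol 7.6.1 continues safety follow-up of implanted subjects after early exit; the summary tables need one stated window

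*SAP*

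**What the plan says.** SAP 6.3.1 (Adverse Events) gives the only general statement of the period over which AEs are reported: "All AEs occurring from when a subject signs informed consent to when a subject exits the study will be accounted for in the reporting". It then defines treatment emergence by a start alone: "A treatment emergent AE (TEAE) is an event on or after the day of surgery". SAP 3.4 does the same. On listings, 6.3.1 says: "All reported adverse events will be detailed in the data listings".

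SAP 2.2 fixes the safety denominator: "The safety analysis set will include all enrolled subjects who undergo CyPass implantation surgery". SAP 5.1 includes among the secondary endpoints: "Rate of intraoperative and post-operative device related ocular adverse events up to 12 months postoperatively". That rate divides subjects with at least one such event by the number of subjects, with no adjustment for follow-up time.

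Protocol 7.6.1 (Terminated Subjects) opens its list of reasons with "Subjects may be terminated (exited) from the study early due to", and AEs are one of the reasons. For implanted subjects it then says: "Subjects who receive the CyPass Micro-Stent but are terminated from the study should be followed for safety until the end of study period". Protocol 6.2 and 7.1 also use *exited* for subjects who leave early.

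**The concern.** The protocol expects safety data from implanted eyes after early exit. The SAP sentence that closes the reporting window stops at exit and does not mention those data. A programmer who takes *exit* in the protocol's sense would cut the AE tables at the termination date. One who works from the treatment-emergent definition, or from the 12-month endpoint, would not. The SAP gives no rule for choosing.

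Under the strict reading an early-exited eye stays in the denominator and is in effect treated as event-free from exit onward. Several of the anticipated postoperative events in protocol 9.2 are defined by late timing: hypotony at 1 month or later, inflammation needing steroid after 2 months, and chronic pain, acuity loss or foreign body sensation at 3 months or later. An eye exited at Month 2 could not count for the 3-month terms, whatever its safety follow-up showed. The study is unmasked (SAP 1.4), so the cut-off is better fixed in text than settled during programming.

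**Working it through.** The point rests on no stated figure. The check sets the passages side by side and then bounds the size.

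**1. Where each element ends**

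- AE reporting window (SAP 6.3.1): study exit.
- Treatment-emergent definition (SAP 3.4 and 6.3.1): starts on the day of surgery, no end.
- Device-related AE rate (SAP 5.1): 12 months after surgery, no exit cut-off.
- Safety follow-up of implanted, terminated subjects (protocol 7.6.1): end of the study period.
- AE listings (SAP 6.3.1): all reported events, no cut-off.
- Listings of secondary surgery and of explantation or repositioning (SAP 6.3.9, 6.3.10): no cut-off.

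The first entry is the odd one out. If exit means early termination, it ends before the protocol's safety follow-up and can end before the 12-month endpoint.

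**2. Direction**

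Let N be the eyes in an arm, x the eyes with at least one event of a given kind, and k the eyes whose first such event comes after exit. The strict rate is (x − k)/N and the full rate is x/N. Since k ≥ 0, the strict rate is never higher, and the shortfall is k/N. N is unchanged because both the safety set (SAP 2.2) and the full analysis set (SAP 2.1) keep every implanted subject who belongs to them, whether or not follow-up is completed.

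**3. Which rates move**

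Take an eye exited at Month 2 with a new event at Month 5.

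- If it exited because of an AE, it is already in the any-AE numerator. If that AE was device-related, it is also in the device-related numerator. The Month 5 event then changes only the count for its own term, or a category not yet met, such as first serious event.
- If it exited for an administrative reason with no earlier event, a device-related event at Month 5 would be its first, and a strict cut-off would remove it from the any-AE and device-related rates too.

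**4. Size**

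Inputs: at least 101 eyes enrolled and 86 completing Month 12 in the two compared groups (protocol 8.1, SAP 7); about 10% lost to follow-up (protocol 5, SAP 7).

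- Non-completers: 101 − 86 = 15 eyes.
- Lost to follow-up: 0.10 × 101 = 10.1, about 10 eyes. Protocol 7.6.1 describes these as not responding to contact, so they yield no later events.
- Non-completers for other reasons: 15 − 10 = about 5 eyes, or 5/101 = 5.0%.
- Assumption, not in the documents: 10% to 50% of those 5 have a first event of the relevant kind after exit. That is 0.10 × 5 = 0.5 to 0.50 × 5 = 2.5 eyes, or 0.5/101 = 0.5 to 2.5/101 = 2.5 percentage points overall.
- If all 5 fell in one arm of about 50 eyes: 0.5/50 = 1.0 to 2.5/50 = 5.0 percentage points in that arm.
- If none has a new event: 0.

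**The case against.** The strongest case on the other side is that the SAP contains no exclusion rule. The 6.3.1 sentence promises to include events up to exit; it does not say that later ones are removed. The treatment-emergent definition and the 12-month endpoint both favour including them. *Exit* is not defined in the SAP, which elsewhere speaks of discontinuation (4.1) and withdrawal (6.3.1), so it could mean the end of all follow-up, safety follow-up included. In that case nothing conflicts. The SAP is also written to protocol Version F, while the protocol supplied is Version D, so 7.6.1 may differ in the governing text. Safety is descriptive (SAP 6.2), and no test depends on this.

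Most of that stands, and it limits the point without removing it. Two readings with no rule to choose between them can give different published rates, and the only meaning of *exit* available in the documents is the protocol's.

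Some stronger readings are tempting, but the documents do not support them:

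- *Events will be collected and then dropped from the arm rates.* This follows only from the strict reading; the SAP does not state it.
- *The data go unused.* All reported events go into the listings.
- *The affected eyes are the highest-risk ones.* Neither document says so. Exit reasons also include voluntary withdrawal and loss to follow-up, and eyes exited for an AE are the ones already counted in the any-AE rate.
- *The omission could reach 7 percentage points overall.* That applies a 50% event share to all 15 non-completers (7.5/101 = 7.4%), including the roughly 10 lost eyes that can supply no later events under any wording.

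**Conclusion.** The mismatch is real and should be corrected. With the protocol's meaning of exit, the SAP's reporting window for the summary tables ends before the safety follow-up that the protocol calls for, and it disagrees with the SAP's own treatment-emergent definition and 12-month rate. Any error runs one way, towards lower AE rates.

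The size is likely small: up to about 5 of 101 eyes exposed to the cut-off, some 0.5 to 2.5 percentage points overall under an assumed 10% to 50% with a new event, and zero if there is none. It would be felt mainly in term-specific counts and in first device-related or first serious events.

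The 5-eye figure assumes that the 10% is entirely loss to follow-up and that every other non-completer was implanted, terminated and still followed. The second assumption is generous, because subjects who withdraw voluntarily may not be reachable. The figure covers only the two compared groups; the documents give no corresponding number for the 30 µl arm. They also give no event rate after exit.

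**What to change.** In SAP 6.3.1, end the window not at exit but *at the end of the subject's safety follow-up, including follow-up after early termination under protocol 7.6.1*. State that such events count in the treatment-emergent summaries. State also that they count in the device-related AE rate if onset is within 12 months of surgery, so that the wider window does not let later events into an endpoint limited to 12 months. Flag events with onset after termination.

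Sections 6.3.9 and 6.3.10 need no change. Confirm the wording against 7.6.1 of protocol Version F before finalising.

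The cost is a short edit to 6.3.1, a changed date cut-off and one flag in the AE programs; the protocol already calls for the data. The small downside is that reported AE rates may be slightly higher.
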